Primary outcome. Phase 1: Outcome assessments will occur at baseline, post-treatment (12 weeks) and follow-up at 2-month post-treatment.

Phase 2: Outcome assessments will occur at baseline, post-treatment (12 weeks) and follow-up at 3 and 12-month post-treatment.

Primary outcome: The participant-rated primary outcome measure is the Victorian Gambling Screen (VGS) harm to self-subscale (Likert scoring 0, 1, 2, 3, 4; range 0-60); a score of 21 and above identifies a person as a problem gambler) relating to the person's experiences in the person's experiences in the previous 4 weeks.

Secondary outcomes: number of days spent gambling and amount of money spent per day gambling will be measured over the previous 1 month, PHQ-9 (depression) GAD-7 (anxiety). WSAS (work and handicap). Other gambling measures include the Gambling Urge Scale (GUS) where higher scores indicate greater urges to gamble with a range 0–42 and the Gambling Related Cognitions Scale (GRCS) which is a 23-item seven-point Likert scale that records the degree of agreement with common thoughts associated with gambling disorder.

Phase 1 Qualitative: Semi-structured interviews with purposefully chosen (age above and below 20, those who improved/recovered/those who dropped out/did not recover) 6 intervention participants and 2 therapists to determine recruitment barriers and enablers, acceptability and feasibility and any improvements to the intervention or delivery and recruitment. Of particular interest will be the on-line and social media strategies used to recruit non help seeking sports betters.

Project duration:

Phase 1 timeline: 2 months set up, 3 months recruitment, 6 months intervention (3 months during recruitment and another 3 months from end of recruitment), 2 months follow up, 2 months data analysis and write up. – total 12 months.

Phase 2 timeline: 2 months set up, 6 months recruitment, 9 months intervention (6 months during recruitment and another 3 months from end of recruitment) 12 months follow up, 3 months data analysis and write up – total 26 months.

Participant selection and activities

Explain how participants will be recruited or how their data will be selected (e.g. for a registry).

Describe sources and methods that will be employed in the identification and recruitment/selection of potential participants (e.g., clinics, referring doctors, adverts, and time periods) or of historical data (e.g. medical records, databases).

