Fidelity: All therapy sessions will be audio recorded and in phase 1 all sessions will be listened to by CIs [name], [name] and [name] and rated using the adapted 10 item checklist which was developed based on the Cognitive Therapy Scale (CTS) which is an 11-item instrument with good reliability when used by experienced clinicians (Young & Beck, 1980), used for a previous SGTS study of CET vs Cognitive Therapy. ([name] et al). In phase 2, 20% of sessions will be randomly selected from early, mid, and late study phases and checked for therapy fidelity.

Baseline differences will be corrected for if required and missing data will be handled by multiple imputation

Sample size and statistical or power issues – Make sure the size and profile of the sample to be recruited is adequate to answer the research question – please provide details:

Phase 2: In our sample size calculations, we assume a correlation between follow-up measures of r 0.7 (Frison & Pocock, 1992). Based on a type I error rate of 5%, power of 90%, two-tailed test, and a VGS standard deviation of 10.2 units ([name] et al., 2010), to detect a significant difference of 8% (i.e. 4.8 points on the scale) in mean VGS scores between the CET and control groups, 50 participants were required in each group. Given the treatment drop-out rate experienced in

the SGTS treatment programme (approximately 35%) we therefore needed to recruit 70 participants in each group of the study giving a total sample size of 140 participants.

How will you measure, manipulate and/or analyse the information collected?

Phase 1 and 2: The primary analysis will use all available data and follow an intent-to-treat principle to investigate any statistically significant differences in primary and secondary outcomes over time between both groups. Secondary analyses will be conducted based on 'as treated' and 'per protocol' approaches within a counterfactual framework using inverse probability weighting (IPW) (Hernan & Hernandez-Diaz, 2012). The IPW uses the inverse of the probability of being in the observed treatment group.

Generalised mixed-effects models will be used in the analysis of repeated measures for primary and secondary continuous and categorical outcomes. Fixed effects (time-invariant variables) in models were intervention group, time in continuous form (intervention period and follow-up), and interaction between group and time.

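### Phase 2 is sized for a difference in mean VGS, but the stated model has continuous time and one group-by-time term, which on its natural reading tests a linear slope instead

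*Protocol*

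**What the plan says.** The sample-size section of the Protocol fixes the Phase 2 target as a difference in level. The calculation is set "to detect a significant difference of 8% (i.e. 4.8 points on the scale) in mean VGS scores between the CET and control groups", with "a VGS standard deviation of 10.2 units", and it states that "50 participants were required in each group". The error rates are given as "Based on a type I error rate of 5%, power of 90%, two-tailed test", and for the repeated measures "we assume a correlation between follow-up measures of r 0.7". Allowing for about 35% treatment drop-out, 70 per group are to be recruited.

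The section on how the information will be analysed is headed for both phases. It describes an intention-to-treat comparison of outcomes over time between the groups, using generalised mixed-effects models. The fixed effects are intervention group, "time in continuous form (intervention period and follow-up), and interaction between group and time".

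The outcome-measures section sets the visits: "Phase 2: Outcome assessments will occur at baseline, post-treatment (12 weeks) and follow-up at 3 and 12-month post-treatment". Taking 12 weeks as 3 months, these fall at about 0, 3, 6 and 15 months. The participant-commitment section adds a questionnaire assessment at session 4. No section names the visit at which the VGS difference is primary.

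**The concern.** In a model with continuous time, the group coefficient is the arm difference at time zero, before treatment. The treatment effect is then carried by the interaction, which is a difference in slopes. Therapy ends by 12 weeks and follow-up runs a further 12 months, so a plausible course is a benefit gained early and then kept or partly lost. A straight line fits that course badly. The last visit has the most leverage, and the end-of-treatment visit counts against the slope.

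The trial could therefore have its stated 90% power for a difference in means and clearly less for the test its model most naturally yields. A real benefit might be reported as null. If most of the benefit were lost by 15 months, the estimated slope could point the wrong way.

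**Working it through.** **Inputs.** Effect 4.8, SD 10.2 (variance 104.04), r 0.7, two-sided 5%, and 50 or 70 per group are from the sample-size section. Visit times 0, 3, 6 and 15 months are from the outcome-measures section. Assumptions of this check: random intercept (equal correlation 0.7), time in months, complete data, and the effect profiles below, because the protocol gives none. Power = Φ(z − 1.96) + Φ(−z − 1.96).

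**1. The plan's own figure.** For a baseline-adjusted comparison of means at one follow-up, the variance factor is 1 − 0.7² = 0.51.
- n = 2 × (1.960 + 1.282)² × 104.04 × 0.51 / 4.8² = 48.4, so 49 per group, in line with the stated 50.
- At 50: SE = √(2 × 104.04 × 0.51 / 50) = 1.457, z = 3.29, power 90.9%. At 70: 97.4%.
- Unadjusted means would need 95 per group and a change score 57. The plan's 50 is therefore a baseline-adjusted mean comparison.

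**2. Single linear slope, baseline unconstrained.** Mean visit time is 6, so the weights are −6, −3, 0, +9 and the sum of squares is 36 + 9 + 0 + 81 = 126.
- SE at 50 = √(2 × 104.04 × 0.3 / (126 × 50)) = 0.0995 points/month. At 70: 0.0841.
- Benefit 4.8 at all three later visits: slope = (−3 × 4.8 + 9 × 4.8)/126 = 28.8/126 = 0.229; z = 2.30, power 63.2%. At 70: z = 2.72, power 77.5%. About 100 per group are needed for 90%.
- The fitted differential change at month 3 is 3 × 0.229 = 0.7 points when the truth is 4.8.
- Benefit 4.8, 4.8, 2.4: slope = (−14.4 + 21.6)/126 = 0.057; power 8.9% at 50 and 10.4% at 70.
- Benefit grows linearly to 4.8 at 15 months: slope 4.8/15 = 0.32; z = 3.22, power 89.5% at 50.
- Sign: the slope is proportional to −3 × (week-12 effect) + 9 × (15-month effect). It reverses only when the 15-month effect is below one third of the week-12 effect. With nothing left at 15 months: −14.4/126 = −0.114, z = −1.15 at 50.

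**3. Single slope, arms constrained to a common baseline.** The information term becomes 270 − (0.7/3.1) × 24² = 139.9, so SE at 50 = √(62.424 / (50 × 139.9)) = 0.0945.
- Constant 4.8: slope = (115.2 − 0.2258 × 24 × 14.4)/139.9 = 0.266; power 80% at 50 and 91% at 70.
- Benefit 4.8, 4.8, 2.4: slope = (79.2 − 0.2258 × 24 × 12)/139.9 = 0.101; power 19% at 50 and 25% at 70.

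**4. Sensitivity (50 per group, constant 4.8 from week 12, baseline unconstrained).**
- Session-4 assessment included at month 1: power 43% if the full effect is present by then, 78% if it is 1.6 points, 89% if there is none yet.
- Exact 12-week timing (2.76 months): 61.5%.
- Random slopes with an assumed SD of 0.2 to 0.6 points/month: 57% down to 31%.
- Four evenly spaced visits over 15 months: 82%, so the uneven spacing explains much of the loss.

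**5. Two slopes with a knot at week 12.** The intervention-period slope difference is 4.8/3 = 1.6 points/month with SE 0.479 at 50; z = 3.34, power 91.6% under a constant effect.

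**The case against.** The strongest reply is that the bracket after the time term names the trial's two phases and may mean two time segments. On that reading the intervention-period slope has about 92% power under a constant effect, and the problem largely disappears. A reader might infer that the two-slope version also falls short of 90%, because a simple two-visit change score does (about 86% at 50 per group). The full four-visit model does not bear that out. What remains is that the text gives one time variable and one interaction, with no knot or second slope, so the single line is the more natural reading.

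Second, the protocol does not say that the interaction coefficient is the confirmatory test, and contrasts at chosen visits could be drawn from a fitted model. A reader might take the slope test as the declared primary test; that is an inference from the listed fixed effects and the stated interest in differences over time. The plan also reports Cohen's d for mean scores and Fisher tests at follow-up, though neither is presented as the primary VGS comparison. Choosing the contrast may be left to an analysis plan. The time coding, however, is stated here, and a straight-line fit would distort visit contrasts taken from it.

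Third, the size depends on the effect profile, on whether baseline is handled (the protocol corrects baseline differences only if required), and on how many participants give data. The 35% is treatment drop-out, so more than 50 per group may contribute. This is why ranges are given.

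Finally, Phase 1 is single-arm and not hypothesis-testing, and Phase 2 is still to be refined. That limits the point to Phase 2 and makes it cheap to settle now.

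**Conclusion.** The mismatch holds for Phase 2 on the single-slope reading: the sample size is for a difference in mean VGS, while the model's treatment term is a difference in linear slopes. With a random intercept, r 0.7 and a 4.8-point effect reached by week 12 and kept, power is about 63% at 50 per group and 78% at 70 (80% and 91% with a common baseline), against about 91% at 50 for the baseline-adjusted mean difference. If half the effect remains at 15 months, it is about 9-10% (19-25% with a common baseline and the full effect still present at 6 months).

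Two stronger conclusions are not supported:
- Any fading reverses the sign. Without a common baseline, reversal needs the 15-month effect to fall below one third of the week-12 effect. Even with none left, the expected z of about −1.15 is short of significance.
- The trial is underpowered whatever the effect looks like. An effect growing linearly to 15 months keeps 89.5%, and the stated 50 per group is sound for the mean comparison.

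The time coding and the primary contrast need to be made explicit on either reading.

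**What to change.** Enter visit as a categorical factor (baseline, week 12, 3 and 12 months post-treatment) with group-by-visit terms. Adjust for baseline VGS or constrain it equal between arms. Name the adjusted mean VGS difference at one visit as the primary contrast, with the other visits as secondary contrasts from the same model.

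Handling baseline matters. The single-visit contrast has about 91% power at 50 per group with it and about 86% if baseline is left unconstrained (variance factor 2 × (1 − 0.7) = 0.6; SE = √(2 × 104.04 × 0.6 / 50) = 1.58, z = 3.04).

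Keep linear or piecewise slopes as a sensitivity analysis. If two segments were meant, state the knot and which term is primary. The cost is analysis wording and a few degrees of freedom; the sample-size calculation can stay as the match for the named contrast. The change should be made before any Phase 2 outcome data are seen, so that it cannot look data-driven.

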Finally, the proportion of participants who have VGS scores in the non-problem gambling range (<21) at 2, 6 or 12 month follow-up will be tested using Fisher's exact test.

Effect size statistics will also be produced for comparisons of mean observed scores (Cohen's d) (Cohen, 2013) and associations of nominal variables (Cramer's V or phi for 2 x 2 contingency table) (Cramer, 1946). For nonparametric between-group tests, the Mann-Whitney statistic will be calculated as a measure of effect size (Conroy, 2012).

Phase 1: qualitative data -Semi-structured interviews with purposefully chosen (age above and below 20, those who improved/recovered/those who dropped out/did not recover) 6 intervention participants and 2 therapists to determine recruitment barriers and enablers, acceptability and feasibility and any improvements to the intervention or delivery and recruitment. Of particular interest will be the on-line and social media strategies used to recruit non help seeking sports betters. These interviews will be conducted by the RA using phone or videoconferencing with set open ended questions

Data linkage –what linkages are planned or anticipated?

No data linkage activities are planned.

What impact will a participant withdrawing have on the data and how will this be responded to?

Data already recorded from the participant will be retained (as per ethics requirements) but marked as not for use in the study.

Results, reporting, outcomes and future plans

Post approval monitoring and reporting

Once you have received ethics and governance authorisation for your research project, there are the following mandatory reporting requirements you must adhere to as per The National Statement chapter 5.5:

- Annual review – this is required annually for the life of the research on the anniversary of the approval date.
- Final report – this is required to be submitted on completion of the research.
- Amendments – any change to the approved protocol must be reported to the lead HREC.

Failure to submit the required reports is a breach of the NHRMC Australian Code for the Responsible Conduct of Research R17, R22, the National Statement chapter 5.5 and the terms and conditions of the ethical approval of the study. This failure to submit the required report may result in the ethics approval being withdrawn and the application closed.

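### The withdrawal rule bars all data already recorded from anyone who withdraws, which contradicts the intent-to-treat primary analysis on all available data

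*Protocol*

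**What the plan says.** Under *What impact will a participant withdrawing have on the data and how will this be responded to?* the protocol gives a one-sentence answer: "Data already recorded from the participant will be retained (as per ethics requirements) but marked as not for use in the study". The sentence does not exempt baseline scores, assessments completed before withdrawal, or participants content for their data to be used. The remark about ethics requirements attaches to keeping the data. Nothing in the document requires that the data go unused.

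Under *How will you measure, manipulate and/or analyse the information collected?*, for Phases 1 and 2 together, the protocol says: "The primary analysis will use all available data and follow an intent-to-treat principle". Generalised mixed-effects models for repeated measures follow. *Accounting for potential bias, confounding factors and missing information* adds that "missing data will be handled by multiple imputation".

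No section reconciles the withdrawal rule with these statements, and none defines withdrawal or separates it from stopping therapy.

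**The concern.** An intent-to-treat analysis keeps every randomised participant in the arm assigned. Mixed models and multiple imputation can do this with incomplete follow-up because they use the partial record: baseline, session scores and any outcome assessment reached. If that record may not be used, nothing is left to model or impute from, and the participant leaves the analysis altogether.

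In Phase 2 this means excluding people after randomisation for a reason that may relate to outcome. Withdrawal could differ by arm. Participants are told about their assigned therapy, and the two arms make quite different demands: CET involves money management and graded exposure to betting cues, while the control involves education, monitoring and goal-setting.

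In Phase 1 the proportion completing the intervention is a stated aim, the pre-post change is meant to inform Phase 2, and low attenders are the planned naturalistic comparison group. Deleting withdrawers could alter all three.

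**Working it through.** **1. The plan's own sample size, to see whether the rule bears on it.** Inputs from *Sample size and statistical or power issues*: two-sided 5%, power 90%, SD 10.2, difference 4.8 points, r = 0.7. With a baseline-adjusted (ANCOVA) variance:

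n per group = 2 × (1 − r²) × [SD × (z0.975 + z0.90) / difference]²
= 2 × 0.51 × [10.2 × (1.960 + 1.282) / 4.8]²
= 0.51 × 94.9 = 48.4, so 49, against 50 stated.

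The stated 50 is reproduced closely, so the sample size is not the issue here.

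**2. Loss of power.** The protocol gives no withdrawal rate, so the rates below are assumptions. The starting point is 70 recruited per group, with the same ANCOVA variance.

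| Withdrawn and excluded | Usable per group | Power |
|---|---|---|
| 0% | 70 | 97.4% |
| 5% | 66.5 | 96.7% |
| 10% | 63 | 95.9% |
| 20% | 56 | 93.7% |

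Power suffers little. The cost of the rule is bias.

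**3. Bias in the Phase 2 difference.** Let w be the share withdrawing in an arm and D the amount by which withdrawers score worse on the VGS than those who remain. The full-arm mean is the remainers' mean plus w × D, so deleting withdrawers lowers the arm's mean by w × D. With the same D in both arms, the shift in favour of CET is

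bias = (w_CET − w_control) × D.

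All values of w and D here are illustrative.

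- Equal w and equal D: bias = 0.
- 20% vs 10%, D = 4: 0.10 × 4 = 0.4 points, and 0.4 / 4.8 = 8% of the target difference.
- 25% vs 10%, D = 8: 0.15 × 8 = 1.2 points, and 1.2 / 4.8 = 25% of the target difference.
- Withdrawers mainly early recoverers: D is negative and the same rates bias against CET.

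These figures compare the analysis without withdrawers with one in which their outcomes are fully known. Scores after withdrawal remain missing even under a better rule, so the figures are an upper limit on what the fix recovers.

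**4. Phase 1.** The *Design* paragraph expects about 65% of 40 to attend four or more sessions (0.65 × 40 = 26) and 35% to have no or minimal intervention (0.35 × 40 = 14). Suppose 6 of the 40 withdraw, are deleted and leave the denominator (an assumption).

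- All six are low attenders (worst case): 26 / 34 = 76% instead of 26 / 40 = 65%, and the comparison group falls from 14 to 14 − 6 = 8.
- Withdrawal is proportional to attendance: about 22 / 34 = 65%, so the proportion does not change.

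**The case against.** The strongest reply is about scope. The rule answers a question about a participant withdrawing, and the protocol elsewhere keeps people who stop therapy. The *Design* paragraph uses non-attenders and low attenders as a comparison group and follows each Phase 2 participant for 12 months, and the qualitative section plans interviews with drop-outs. A reader might infer that the rule turns the primary analysis into one of therapy completers. The documents do not support that. On the natural reading the conflict is confined to people who leave the study. What remains is that withdrawal is undefined, so staff could apply the rule to someone who only stops sessions.

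A reader might also take the roughly 35% in the sample size section as the share of data lost. That figure is treatment drop-out. It is not a withdrawal rate and plays no part here.

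It can also be said that size and direction are assumed. This stands. The bias may be zero or run against CET, and a flat statement that the rule inflates the CET effect or the Phase 1 pre-post change would go too far. The 76% is a worst case, and the protocol does not state that withdrawers leave the completion denominator. Phase 1 is also described as not hypothesis testing, so no confirmatory claim is at risk there.

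Finally, data marked as not for use could be called not available, which would square the rule with the words on available data. It would not square it with intent to treat, which requires that randomised people stay in the analysis. Nor can this be left to a statistical analysis plan: such a plan could not properly use data that the approved protocol says are not for use.

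**Conclusion.** The concern holds for participants who withdraw from the study. The withdrawal rule and the stated primary analysis cannot both be followed, and this conclusion needs no assumption about rates.

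The size of the consequence does rest on assumptions. In Phase 2 the bias is zero with equal withdrawal and equal excess, about 0.4 to 1.2 VGS points under the illustrative 20–25% versus 10% with 4–8 points excess, and opposite in sign if withdrawers are mainly early recoverers. Loss of power is minor. In Phase 1, with six withdrawals, adequate-dose attendance could read up to 76% instead of 65% and the comparison group could shrink from 14 to 8, but only if all six are low attenders and are dropped from the denominator.

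The confirmatory consequence lies in Phase 2. The Phase 1 consequence is for the feasibility figures and the effect estimate carried forward.

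**What to change.** Replace the sentence with wording such as: *Data collected up to the point of withdrawal are kept and used in all analyses unless the participant specifically asks for their removal. Stopping therapy is not withdrawal from the study, and those participants continue to be sent follow-up questionnaires.*

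In addition:

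- Report withdrawals, and any requests for removal of data, by arm in Phase 2.
- Keep all consented participants (Phase 1) and all randomised participants (Phase 2) in the denominators.
- Check that the participant information and consent form says the same. Its text is not among the pages at hand, so whether it already does cannot be judged here.

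The cost is a short ethics amendment, with a matching change to the consent form if needed. No extra participants or study procedures are required. Scores after withdrawal will still be missing, so the change removes the contradiction and an avoidable part of the bias, not all of it.
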